6.7 Prior and Concomitant Medications

All prescription, nonprescription medications (e.g., over-the-counter [OTC]) drugs and herbal supplements) and non-medical treatments starting from 30 calendar days before Screening until end of the study must be recorded in source documents and the eCRF. For each medication, documentation should list the trade or generic name, the total daily dose including units (or the dose, units, and scheduled and actual frequency of administration if the medication is not taken daily), the route of administration, and the reason for use.

Changes, additions, or discontinuations to medications will be assessed and recorded in the eCRF during each study visit. All as-needed prescriptions should be converted to reflect actual dose taken per day.

Starting on the first day of the screening phase, after written informed consent for the study has been provided, all antipsychotic or other psychotropic medications will be stopped with clinically appropriate titration down as per the Investigator's clinical judgment. Patients will be

Confidential Page 49 of 102

instructed not to take any medication(s) during the conduct of the study unless approved by the Investigator. Any patient unable to be safely discontinued from current antipsychotic therapy or other psychotropic medications will not be eligible for the study. Any treatment other than the study treatment given will be considered a concomitant medication and will be documented in the eCRF. Any patient requiring emergency treatment with prescription or nonprescription medication during the screening phase through the EoS Visit will be approved by the Investigator. If the Investigator determines that the patient requires medication during the study, the Medical Monitor must be contacted within 24 hours.

Psychotropic medications are prohibited except for lorazepam as needed for agitation, restlessness, irritability, or hostility; zolpidem, zaleplon, or eszopiclone for insomnia; diphenhydramine or benztropine for EPS; and propranolol for akathisia.

Within the daily limits shown in 2, lorazepam, benztropine, and propranolol are not allowed on as needed basis; every administration must be considered and approved by the Investigator prior to administration.

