Vital Signs ^t	X	X		X		X		X		X		
Adverse Events ^u	X	X	X	X	X	X	X	X	X	X	X	X
Other												
Study Drug Dosing		X	X	X	X	X	X	X	X	X		
PK Sample Collection ^v		X		X				X				
Restart Standard Antipsychotic ^w											X	

a. Screening begins when the ICF is signed and will take place between Day -7 and Day -1; up to a 7-day extension of the screening phase is allowed, if necessary with the approval of the Medical Monitor; screening procedures should be initiated with a sufficient amount of time allotted in order to obtain central laboratory results and ECG results from the central reader prior to randomization. Review of inclusion/exclusion criteria at Baseline will be based on assessments performed during Screening. Hospitalization will begin with the signing of the ICF for patients who are not already hospitalized at the initial Screening Visit.

Confidential Page 55 of 102

Each patient may receive the QD administration of study treatment. No other assessments are scheduled; however, AEs observed or reported, and concomitant medications may be recorded. In case of an AE, an unscheduled visit may be conducted at the discretion of the PI.

c. Stabilization Period is up to 5 days.

d. The Screening assessments to be audio recorded include the MINI 7.0.2, PCRS and SCI-PANSS and are submitted to an independent central reviewer for review and eligibility confirmation.

^{e.} Includes full psychiatric history, DSM-5 diagnosis of schizophrenia, and MINI 7.0.2.

Washout of prohibited medications begins after signing the ICF and after diagnosis of Schizophrenia is confirmed by MINI. Details of medications requiring washout and guidance for washout time required are provided in Appendix 14.4. Prohibited and restricted medications are listed in Table 6.3:

g. Urine drug screen (full panel including opioids) and a blood alcohol test are required at the designated times, but either or both can be conducted at any time during the trial at the discretion of the Investigator.

h. At Screening, Baseline, and final endpoint, SCI-PANSS and CGI-S will be evaluated by a local site rater with central supervision via independent, central review.

SCI-PANSS will be audio recorded at any visit where they are administered. SCI-PANSS assessment should be preceded by the PCRS. Patients with improvement of ≥20%

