- Important note: Free T4 will be measured only if the result for TSH is abnormal.
- 5. Standard 12-lead ECGs (in triplicate) will be performed after the patient has been supine and at rest for ≥5 minutes. The captured ECGs must be separated by at least 1 minute. A central ECG service will be utilized to review all ECGs in order to standardize interpretations for the safety analysis. In addition, ECG results will be evaluated at the investigational site to monitor safety during the trial. Any Screening ECG with abnormal result(s) considered to be clinically significant should be repeated to confirm the finding(s) before excluding the patient from the trial. Patients will be randomized based on Screening ECG results from the central reader and Baseline ECG results from the trial site. If the Baseline ECG results from the central reader, when available, indicate a QTcF >450 msec at Baseline, the Investigator must contact the Medical Monitor to discuss the patient's continued participation in the trial. ECGs scheduled for the same visit as blood samples are to be completed before blood is drawn.
- Vital signs will include body temperature, SBP, DBP, and heart rate. Blood pressure and heart rate will be measured in the following order: supine, sitting and standing after the patient has been in each position for at least 3 minutes. Vital signs scheduled for the same visit as blood sample have to be completed before blood is drawn.

Confidential Page 56 of 102

- The recording of AEs is to start immediately after the ICF is signed and up to 14 days after the end of EoT.
- PK analyses will include the First 60 randomized patients regardless of cohort. PK blood samples will be collected on Day 1, 8, and 21 during the following timepoints after the morning dose: 15 minutes, 30 minutes, 1, 2, 3, 4, 8, and 24 hours. See protocol Section 8.3. On Day 1 only, a pre-dose PK blood sample will be collected. Samples are collected after ECGs and vital signs. The total volume of blood to be collected during the Screening, treatment, and End of Stabilization period is 161 mL. Approximately 21 mL of blood will be collected during the Screening Visit, 130 mL will be collected during the 28-day Treatment Period, and 10 mL will be collected during the End of Stabilization period.
- w. On Day 29 patients are to be started on standard antipsychotic medication as prescribed by the Investigator.

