## 2.3 Estimands

The primary study estimand is described in Table 1 below.

**Table 1.** Primary Study Estimand: PANSS Total Score at Week 4

Objective: To determine whether LB-102 [REDACTED] administered to patients with acutely exacerbated schizophrenia demonstrates antipsychotic efficacy as determined by a change from Baseline on the PANSS total score, compared to placebo	
Estimand: Treatment effect of LB-102 vs Placebo regardless of intercurrent events (treatment-policy)	
Treatment: LB-102 (50 mg or 75 mg) and matching Placebo	
ESTIMAND	ANALYSIS
Target population	Analysis set
Adult patients with acute schizophrenia as identified by the study eligibility criteria	Intent-to-Treat (ITT) analysis set, defined as all randomized patients.  Should the ITT and modified ITT (mITT) analysis sets overlap substantially (i.e. 95% of patients in the former are also in the latter), the mITT will be considered as the reference analysis set for all estimand-related analyses.
Variable	Outcome measure
PANSS Total Score at Week 4	Change from Baseline to Week 4 in the PANSS total score
Handling of intercurrent events	Handling of missing data

 
• Taking a prohibited medication prior to Week 4
 
• Starting an emergency treatment prior to Week 4
 
 
All of these intercurrent events (ICEs) will be handled via a treatment-policy strategy, i.e. data collected after their occurrence will be included in the statistical analysis of the endpoint.
	
All missing data due to study discontinuation for lack of efficacy or drug-related adverse events (AEs) will be imputed assuming a Missing Not at Random (MNAR) mechanism and assuming that after withdrawal the patients revert to the distribution of the worst PANSS score values observed up to time of discontinuation, whereas missing data due to discontinuation for any other reason, will be imputed under a Missing at Random (MAR) assumption using a Multiple Imputation (MI) approach.
 
As a sensitivity analysis, missing data that was imputed under a MAR mechanism in the primary analysis will be imputed under a MNAR mechanism using a tipping-point approach to check robustness of the main analysis

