## **5.8 Prior and Concomitant Medications**

Prior medications are defined as all medications that were stopped in the 30 days before ICF sign-off, whereas concomitant medications are defined as medications taken on or after such date.

Separate tabulations will be produced for prior and concomitant medications presented by actual treatment group and overall for the Safety Analysis Set. Concomitant medications will be coded using the WHO dictionary (version B3 Global Mar-2023 or later) and summarized using Anatomic Therapeutic Chemical (ATC) Level 2.

Prior medication washout information will also be listed separately.

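### The concomitant medication table runs from consent with no end date, so it cannot show on-treatment medication use by arm

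*SAP*

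**What the plan says.** SAP 5.8 uses consent as the only dividing line. On one side, "Prior medications are defined as all medications that were stopped in the 30 days before ICF sign-off". On the other, "concomitant medications are defined as medications taken on or after such date". Neither first dose nor last dose is mentioned. Separate tabulations of the two classes are planned by actual treatment group for the Safety Analysis Set. They appear in SAP Section 10 as Tables 14.1.3.3 (prior) and 14.3.8 (concomitant), and neither title shows a split by study period.

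The protocol places several kinds of use after consent:

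- **Screening.** From the first day of screening, after consent, "all antipsychotic or other psychotropic medications will be stopped with clinically appropriate titration down" (Protocol 6.7). A footnote to the schedule in Protocol 7.1 agrees: "Washout of prohibited medications begins after signing the ICF and after diagnosis of Schizophrenia is confirmed by MINI".
- **Treatment, Days 1 to 28.** Lorazepam, benztropine and propranolol are permitted within limits (Protocol Table 6.2). Other use may be prohibited or emergency medication.
- **Stabilization, up to Day 33.** "On Day 29 patients are to be started on standard antipsychotic medication as prescribed by the Investigator" (Protocol 7.1). Lorazepam, benztropine and propranolol are unrestricted in this period (Protocol 6.7).
- **Recording.** Medications "starting from 30 calendar days before Screening until end of the study must be recorded in source documents and the eCRF" (Protocol 6.7). The last visit is at Day 42 ± 2.

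SAP 2.3, Table 1, names two intercurrent events for the primary estimand. One is "Taking a prohibited medication prior to Week 4" and the other is starting emergency treatment before Week 4. Both are handled by treatment policy, so data collected after them stay in the analysis.

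**The concern.** A by-arm medication table normally lets a reader see what else patients took while the randomized treatments were being compared. That matters here because the primary result is a treatment-policy estimate. If more placebo patients than active patients received prohibited or emergency medication before Week 4, the Week 4 difference in PANSS total score includes the effect of that medication. The reader needs the frequency by arm to judge this.

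As defined, the table mixes protocol-directed use outside the treatment period with use inside it. The same applies to benztropine and propranolol, which are given for extrapyramidal symptoms and akathisia. Their on-treatment use bears on a named safety domain, but they are also allowed in screening and unrestricted in stabilization.

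The prior table is affected too. An antipsychotic still being taken at consent was not stopped before consent, so it drops out of the prior table and appears only as concomitant.

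**Working it through.** **1. Classification under the rule as written**

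| Use | Class under SAP 5.8 | Overlaps Days 1–28? |
|---|---|---|
| Antipsychotic stopped in the 30 days before consent | Prior | No |
| Antipsychotic taken at consent, washed out in screening | Concomitant | No |
| Prohibited antipsychotic taken on, say, Day 14 | Concomitant | Yes (intercurrent event) |
| Standard antipsychotic started on Day 29 | Concomitant | No |
| Benztropine in screening only, or on Day 10, or on Day 30 | Concomitant in all three cases | Only Day 10 |

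The table does not distinguish the second to fourth rows by time, nor the three benztropine cases.

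**2. Span of the concomitant window**

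Inputs from Protocol 7.1: screening of 7 days, extendable by up to 7; treatment on Days 1 to 28; end-of-study visit at Day 42 ± 2.

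- Shortest: 7 + 42 = 49 days (7.0 weeks).
- Longest: 14 + 42 = 56 days (8.0 weeks). This reproduces the protocol's stated maximum of about 8 weeks. With the +2-day visit window it is 58 days.
- Treatment share: 28/49 = 57% to 28/56 = 50%.
- Outside treatment: 49 − 28 = 21 to 56 − 28 = 28 days, or 43% to 50%. This is 7 to 14 days before the first dose plus 14 days after the last.

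These spans are for a patient who completes the study.

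**3. How pooling could mask a difference**

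The documents give no rates, so this is an illustration with assumed values. Let *p* be the share of an arm using an antipsychotic on treatment. Let *r* be the share using one in screening or from Day 29, taken as equal in both arms and independent of on-treatment use. The tabulated any-use share is 1 − (1 − *p*)(1 − *r*), and the gap between arms shrinks to (*p* placebo − *p* active)(1 − *r*). Assume *p* = 5% on active and 15% on placebo, a true gap of 10 points:

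| *r* | Active | Placebo | Gap shown (points) |
|---|---|---|---|
| 0% | 5% | 15% | 10 |
| 50% | 52.5% | 57.5% | 5.0 |
| 75% | 76.25% | 78.75% | 2.5 |
| 90% | 90.5% | 91.5% | 1.0 |
| 100% | 100% | 100% | 0 |

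The direction is certain if *r* is above zero. The amount depends entirely on *r*.

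**4. Other planned outputs**

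- Listing 16.2.4.9 gives concomitant medications by patient, and listed dates are as recorded on the eCRF (SAP 5.2.6). Washout is listed separately (SAP 5.8).
- Table 14.1.1.5 summarizes protocol deviations by class and reason (SAP 5.5). Protocol 10.4.1 gives receipt of a prohibited concomitant treatment as an example category.
- The responder analysis (SAP 2.3, Table 2, and SAP 5.11.5.5) needs both intercurrent events identified for each patient, but it absorbs them into non-response and does not display them.
- The list in SAP Section 10 has no table of the intercurrent events.

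**The case against.** The other side has several sound points.

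- **Visibility.** A reader might infer that use during the 28 days cannot be seen at all. The documents do not support that. The dated listings show it patient by patient, the responder analysis requires the flags, and Protocol 6.7 asks for the amount and timing of each lorazepam, benztropine or propranolol administration.
- **Other tables.** A reader might infer that no other planned table bears on the question. The deviation summary does: protocol-directed washout and the Day 29 restart are not deviations, so it would largely separate prohibited use from them. It is only a partial substitute. It is not limited to the period before Week 4, the protocol's categories are examples only, and SAP 5.5 does not itself say that the table is by arm. Emergency treatment approved by the Investigator need not be a deviation.
- **Size.** A reader might infer that antipsychotic use would approach 100% in every arm by construction. This cannot be derived. Drugs stopped before consent count as prior, Protocol 7.2.11 says antipsychotics may be started on Day 29 where the schedule footnote says they are to be started, and the documents do not say how much medication will be recorded after withdrawal, with 25% drop-out assumed.
- **Consistency with the protocol.** Protocol 6.7 treats any treatment other than study treatment as concomitant, so the SAP definition is not a contradiction. That stands. However, a broad recording rule does not require a summary table without periods. The SAP anchors elsewhere on dosing: treatment-emergent events (SAP 5.13.1) and imputed medication start dates (SAP 5.2.6) both refer to first dose.
- **No effect on estimates.** Correct. Table 14.3.8 feeds no model or test.

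**Conclusion.** The point holds as a reporting weakness. Followed as written, SAP 5.8 yields a concomitant medication table that covers 49 to 56 days for a completer, of which 28 are treatment, and it cannot show on-treatment use by arm. That use is recoverable only from dated listings and, in part, from the deviation summary. No dedicated by-arm summary of the two intercurrent events is planned. The primary estimate and its test do not change; what suffers is the reader's ability to interpret a treatment-policy result. The extent of masking is unknown, and the illustration above rests on assumed rates, equal outside use in the arms and independence. This is a worthwhile improvement, not an essential correction.

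**What to change.** In SAP 5.8, replace the consent-based rule with three classes built from dates already collected, and tabulate each by arm:

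- **Prior:** stopped before first dose.
- **On-treatment:** taken at any time from first to last dose, whenever started.
- **Post-treatment:** started after last dose.

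Add one by-arm table with the number and percentage of patients with prohibited medication before Week 4 and, separately, with emergency treatment before Week 4, using the flags that the responder analysis already requires. This table is needed as well as the split, because in a patient who stops dosing early an intercurrent event can fall after the last dose but before Week 4.

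The cost is SAP wording and a small amount of extra output. No new data are needed.

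The protocol's statements on when earlier psychotropics are discontinued should also be reconciled. Inclusion criterion 10 (Protocol 5.1) refers to discontinuation before Screening, whereas Protocol 6.7 and the washout footnote in Protocol 7.1 place it after consent. Under the current SAP rule, that timing decides whether such a drug counts as prior or concomitant.

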## **5.9 Exposure to Study Drug**

Extent of exposure will be summarized descriptively by actual treatment group for the Safety Analysis Set, including the following parameters:

- Length of exposure (days)
- Number of doses received
- Number of doses missed

## **5.10 Treatment Compliance**

Treatment compliance will be summarized descriptively by treatment groups for the Safety Analysis Set. In addition, the categories of compliance defined in Section 5.2.8 will also be summarized with counts and percentages.

## **5.11 Efficacy Analyses**

Statistical tests will be performed using a two-tailed 5% overall significance level, unless otherwise stated. For the primary analysis of the primary endpoint, a multiplicity strategy will be in place to ensure that the familywise error rate (FWER) is controlled at this level across the doses tested (see Section 5.11.7 for details).

All comparisons between treatments will be reported with 95% confidence intervals for the difference.

### **5.11.1 Primary Endpoint**

The primary endpoint is the change from Baseline to Week 4 in the PANSS total score. The null hypothesis associated with this endpoint is that the decrease from Baseline to Week 4 in either the LB-102 50 mg or 75 mg arms are equal or smaller than what observed in the Placebo arm, and the alternative being that the decrease in the active arm is larger than in the Placebo arm. This set of hypotheses can be formalized as follows:

#### LB-102 50 mg arm:

$$H_0: \mu_{LB-102\ 50\ mg} \geq \mu_{Placebo}$$

$$H_1: \mu_{LB-102\ 50\ mg} < \mu_{Placebo}$$

#### LB-102 75 mg arm:

$$H_0: \mu_{LB-102\ 75\ mg} \geq \mu_{Placebo}$$

$$H_1: \mu_{LB-102\ 75\ mg} < \mu_{Placebo}$$

No formal hypothesis will be tested for the LB-102 100 mg arm, but data will be included in any analysis model for all the primary and secondary efficacy endpoints and CIs and p-values provided for descriptive purposes.

Methods to control type I error rate at the nominal 5% level are described in Section 5.11.7.

### **5.11.2 Primary Efficacy Analysis**

In line with the primary study estimand, prior to performing the statistical modelling missing data due to a discontinuation related to either lack of efficacy or drug-related AEs will be imputed assuming a MNAR mechanism whereas missing data due to discontinuation for any other reason or non-monotone missing data will be imputed under a MAR mechanism.

The MAR imputation will use a fully conditional specification approach with a predictive mean matching (PMM) method, where a missing value is imputed using a value randomly selected from a set of  $k$  ( $= 5$ ) observed values that are the closest to the predicted value for the missing data point. This imputation will be performed using the following SAS code:

```

proc mi data =  n impute = 100 seed = 99 out = impute01 minimum
= 30 maximum = 210 round = 1;
  by trt01p;
  var baseline week_1 week_2 week_3 week_4;
  fcs nbiter = 1000 regpmm( baseline);
  fcs nbiter = 1000 regpmm(week_1 = baseline);
  fcs nbiter = 1000 regpmm(week_2 = baseline week_1);
  fcs nbiter = 1000 regpmm(week_3 = baseline week_1 week_2);
  fcs nbiter = 1000 regpmm(week_4 = baseline week_1 week_3);
run;

```

Missing values for patients dropping out from the study because of lack of efficacy or drug-related AEs will be imputed iteratively assuming that after withdrawal the patients will follow the distribution of the worst values observed up to the study visit at which they withdraw. A schematic illustration of the process would be as follows:

- All patients with non-missing Week 1 PANSS score values (including both those with an actual observed Week 1 value and those who had this value imputed as part of the MAR imputation step described above) will have a variable (WORST1) calculated which is the maximum PANSS score values observed between baseline and Week 1, whereas those with a missing Week 1 value will have a missing value for WORST1 as well
- The imputation step will use WORST1 as the variable to be imputed and baseline and Week 1 values as predictors using the PMM method described above for the MAR imputation step. Patients with a missing Week 1 value will thus have their Week 1 value imputed by the WORST1 value predicted by the imputation procedure.
- A similar approach will thus be followed for Week 2, i.e. creating a WORST2 variable, imputing it using a PMM approach and using this imputed value as the Week 2 value for patients with a missing assessment at that visit.
- This approach will then be repeated for Week 3 and 4, until at last all values missing because of lack of efficacy or drug-related AEs have been imputed/replaced.

The below sample SAS code implements the above steps, with the input dataset of the first DATA STEP being the output dataset of the PROC MI step above and including the patient ID and the MAR-imputed PANSS data in wide format, one column for timepoint, i.e. baseline, Week 1, 2, 3 and 4:

```

* Create WORST1 variable;

data step1;
  set analysis02;
  if not missing(week_1) then worst1 = max(baseline, week_1);
run;

* Impute WORST1 for patients with missing Week 1 data;

```

```

proc mi data = step1 nimpute = 1 seed = 99 out = step2a minimum = 30 maximum
= 210;
  by _imputation;
  var baseline worst1;
  fcs nbiter = 1000 regpmm(worst1 = baseline);
run;

* Set Week 1 = WORST1 for missing data and create WORST2 variable;

data step2b;
  set step2a;
  week_1 = ifn(missing(week_1), worst1, week_1);
  if not missing(week_2) then worst2 = max(baseline, week_1, week_2);
run;

* Impute WORST2 for patients with missing Week 2 data;

proc mi data = step2b nimpute = 1 seed = 99 out = step3a minimum = 30 maximum
= 210;
  by _imputation;
  var baseline week_1 worst2;
  fcs nbiter = 1000 regpmm(worst2 = baseline week_1);
run;

* Set Week 2 = WORST2 for missing data and create WORST3 variable;

data step3b;
  set step3a;
  week_2 = ifn(missing(week_2), worst2, week_2);
  if not missing(week_3) then worst3 = max(baseline, week_1, week_2, week_3);
run;

* Impute WORST3 for patients with missing Week 3 data;

proc mi data = step3b nimpute = 1 seed = 99 out = step4a minimum = 30 maximum
= 210;
  var baseline week_1 week_2 worst3;
  fcs nbiter = 1000 regpmm(worst3 = baseline week_1 week_2);
run;

* Set Week 3 = WORST3 for missing data and create WORST4 variable;

data step4b;
  set step4a;
  week_3 = ifn(missing(week_3), worst3, week_3);
  if not missing(week_4) then worst4 = max(baseline, week_1, week_2, week_3,
week_4);
run;

* Impute WORST4 for patients with missing Week 4 data;

proc mi data = step4b nimpute = 1 seed = 99 out = step5a minimum = 30 maximum
= 210;

```

```

var baseline week_1 week_2 week_3 worst4;
fcs nbiter = 1000 regpmm(worst4 = baseline week_1 week_2 week_3);
run;

* Set Week 4 = WORST4 for missing data;

data step5b;
set step5a;
week_4 = ifn(missing(week_4), worst4, week_4);
run;

```

Upon completion of the above imputation steps, the change from baseline in the PANSS score will be derived and used in the statistical modelling. To such aim, a MMRM will be fit for each imputed dataset, including pooled study site, visit, treatment and treatment by visit interaction as categorical effects and Baseline PANSS total score as continuous covariate and the change from Baseline in the PANSS total score at 1, 2, 3 and 4 weeks after baseline as response. Correlation between repeated observations within a patient will be accounted for via an unstructured correlation matrix, however, should this structure lead to convergence issues, the following decreasingly complex alternative structures will be fit in turn until the model converges: Toeplitz, first-order autoregressive, and compound symmetry. The assessment of model convergence will be done prior to unblinding. The LS means for change from Baseline to all post-Baseline timepoints in the PANSS total score and their differences between the active treatment arms (50 and 75 mg) and placebo will be estimated for each imputed dataset. Model assumptions will be examined graphically for a random selection of 10% imputations (i.e. 10) via inspection of conditional residuals scatterplots (residuals vs predicted values), quantile-quantile plots and histograms. Should any substantial violation be observed, non-parametric analyses (e.g. Wilcoxon rank-sum test) will be adopted, and this decision will be documented based on blinded data prior to database lock. This model will be fit using the example SAS code below:

```

ods output estimates = est LMeans = lsm diff = diff;
proc mixed data =  plots (only) = studentpanel(marginal);
by _imputation_;
class subjid trt01pn avisitn siteid;
model chg = trt01pn siteid avisitn trt01pn*avisitn base / ddfm = kr;
repeated avisitn / type = un subject = subjid;
lsmeans trt01pn*avisitn / diff cl;
run;

```

The model estimates (LS means and their differences between treatment arms) will be pooled using Rubin's combination rules to incorporate the between-imputation with the within-imputation variability and to obtain one single point and interval treatment effect estimate for each active arm using the PROC MIANALYZE procedure. The below sample SAS code implements the pooling across imputations:

```

proc mianalyze data = ;
by trt01pn avisitn;

```

```
modeleffects estim;
stderr sem;
ods output parameterestimates = parmest;
run;
```

where *estim* and *sem* are the point and variability estimates from the MMRM analysis for each imputed dataset for each relevant parameter. In the above code, the BY statement ensures that the pooling is done across imputations within each level of TRT01PN and AVISITN (these variable names might change depending on the actual variable used in the analysis). LS means and their differences between the active arms and Placebo alongside 95% CIs and p-values for the differences will thus be reported after the above pooling has been done, inclusive of the results of the multiplicity adjustment procedure described in Section 5.11.7. The estimated LS means over time will be graphically displayed alongside their 95% CI in a line plot. A descriptive summary of PANSS total scores and their changes from baseline will also be presented.

This analysis (inclusive of the graphical representation) will be performed for the ITT analysis set and repeated also for the mITT Analysis Set, however should the two analysis sets overlap substantially (i.e. if at least 95% of the patients in the ITT are also included in the mITT) the primary analysis will be performed for the mITT and the ITT only be regarded as supportive information.

All PANSS score data, inclusive of individual items responses as well as subscale scores, will also be listed.

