### 3 SAMPLE SIZE

[REDACTED] patients will be randomized in a 3:3:3:1 ratio to placebo, LB-102 50 mg QD, LB-102 75 mg QD, or LB-102 100 mg QD, respectively, with [REDACTED] patients randomized to each of the first 3 arms and [REDACTED] to the last one (LB-102 100 mg). This will ensure at least 85% power at a 2-sided 5% significance level to detect a treatment difference on the primary endpoint of 8 between either LB-102 50 mg or 75 mg and placebo QD, assuming a common SD of 18, an overall drop-out rate of 25% and a Hochberg procedure to adjust for multiplicity. The sample size was estimated via Monte Carlo simulations using 10,000 simulated trials.

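### The prescribed MAR imputation line for Week 4 PANSS leaves out Week 2 without explanation and may pull some imputed primary-endpoint values towards the arm's predicted mean

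*SAP*

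**What the plan says.** SAP 5.11.2 introduces the MAR block as prescribed code: "This imputation will be performed using the following SAS code". The block is run separately by treatment arm, uses predictive mean matching, and lists all visits: "var baseline week_1 week_2 week_3 week_4". The visit models then read:

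- Week 2: "fcs nbiter = 1000 regpmm(week_2 = baseline week_1"
- Week 3: "fcs nbiter = 1000 regpmm(week_3 = baseline week_1 week_2"
- Week 4: "fcs nbiter = 1000 regpmm(week_4 = baseline week_1 week_3"

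Weeks 2 and 3 each use every earlier visit. Week 4 skips Week 2, and no reason is given. In the worst-value step of the same section, the corresponding model is "fcs nbiter = 1000 regpmm(worst4 = baseline week_1 week_2 week_3", which includes it.

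The MAR block is not meant to settle every dropout, because "missing data due to a discontinuation related to either lack of efficacy or drug-related AEs will be imputed assuming a MNAR mechanism". MAR covers the other discontinuation reasons and non-monotone gaps. The primary MMRM, also in 5.11.2, uses an unstructured within-patient matrix.

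**The concern.** An imputation model should be at least as rich as the analysis model, and MAR is credible only if the imputation conditions on the observed history. The Week 4 line forces the direct contribution of Week 2 to zero. If Week 2 carries information about Week 4 beyond Baseline, Week 1 and Week 3, imputed Week 4 values are drawn too close to what those other visits predict.

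The values are used in three places: the primary MMRM (5.11.2), the tipping-point analysis, which adds its shifts to them (5.11.3.2), and the PANSS responder status obtained by dichotomising them (2.3 Table 2 and 5.11.5.5).

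A smaller matter lies in the same block. Each line names earlier visits only, so an intermittent gap is filled without the patient's later observed scores.

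**Working it through.** **Inputs from the documents.** The four code lines above; Week 4 SD 18, planned difference 8 and overall dropout 25% (SAP section 3). The documents give no visit correlations, no SDs before Week 4, and no dropout by visit or reason. Those are assumed below. There is no stated figure to reproduce.

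**Who is touched.**
- Leaves after Week 1: no observed Week 2 exists to be lost.
- Leaves after Week 2: Week 3 is imputed from the observed Week 2, and Week 4 from that imputed Week 3. Week 2 acts only indirectly.
- Leaves after Week 3: the last score is in the Week 4 model, but the observed Week 2 is unused.

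**Formula for a patient leaving after Week 2.** Hold Baseline and Week 1 fixed.
- Correct weight of Week 2 on Week 4: its coefficient in the regression of Week 4 on Baseline, Week 1 and Week 2.
- Weight implied by the code: (coefficient of Week 2 in the Week 3 model) × (coefficient of Week 3 in the Week 4 model without Week 2).
- Shortfall: the first minus the second, times the Week 2 deviation.

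**By hand, assumed SDs 15/17/18 at Weeks 2, 3 and 4.**

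Exchangeable, r = 0.65. With three predictors the standardised coefficient is 0.65/(1 + 2 × 0.65) = 0.65/2.30 = 0.2826.
- Correct: 0.2826 × 18/15 = 0.339.
- Code: (0.2826 × 17/15) × (0.2826 × 18/17) = 0.096.
- Shortfall: 0.339 − 0.096 = 0.243, that is 2.4 points per 10, or about 3.7 points for a Week 2 score 15 points off expectation.

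First-order autoregressive, r = 0.8.
- Correct: 0.8² × 18/15 = 0.768.
- Code: (0.8 × 17/15) × (0.8 × 18/17) = 0.768.
- Shortfall: 0.

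**Across structures, equal SDs, r from 0.5 to 0.9.**

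| Assumed correlation | Week 2 effect carried | Shortfall per 10 points |
|---|---|---|
| AR(1) | 100% | 0.0 |
| AR(1) plus noise (0.85 × r^lag) | 70–84% | 0.3–1.5 |
| Half AR(1), half exchangeable | 64–80% | 1.0–1.2 |
| Exchangeable | 25–32% | 1.9–2.2 |

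**Effect on the treatment difference, large-sample simulation.** 400,000 patients per arm, exchangeable case, dropout after Week 2 depending on the Week 2 score, with assumed rates of 6.4% on placebo and 2.7% on LB-102.
- Leavers' mean Week 4, imputed against true: 88.2 against 90.5 (placebo), 80.6 against 82.8 (LB-102).
- Shift in arm means: 0.064 × (−2.3) = −0.147 and 0.027 × (−2.2) = −0.059.
- Shift in the difference: −0.059 − (−0.147) = +0.088, so −8.00 becomes −7.91.

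**Effect with predictive mean matching at trial size.** Assumed 108 per arm, five donors, 500 simulated trials per arm, 12–16% leaving after Week 2 with probability rising with the score. Negative leaver error means too favourable. The Monte Carlo standard error of the bias in the difference is 0.03 to 0.04.

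| Structure | Placebo leavers' error: code / fixed | Bias in difference: code / fixed |
|---|---|---|
| AR(1) 0.8 | −1.43 / −1.60 | 0.06 / 0.08 |
| AR(1) plus noise 0.9 | −1.80 / −1.26 | 0.07 / 0.07 |
| Half and half 0.8 | −1.73 / −1.13 | 0.09 / 0.06 |
| Exchangeable 0.7 | −2.20 / −1.11 | 0.12 / 0.07 |
| Exchangeable 0.5 | −2.09 / −0.85 | −0.01 / −0.02 |

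Some leaver error remains after the fix because matching finds few donors at high scores. Both simulations treat every leaver as MAR.

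**The case against.** A reader might infer that patients who leave after a poor Week 2 are certain to receive Week 4 values that flatter them, and that the primary result is materially biased. The documents do not support this, for four reasons.

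- **The effect is conditional and symmetric.** It needs Week 2 to predict Week 4 beyond the other visits. Under first-order dependence there is none, and a better-than-expected Week 2 errs the other way.
- **Many of the worst cases go elsewhere.** Lack of efficacy, which protocol 5.3 describes as worsening psychosis, is assigned to worst-value imputation. MAR keeps reasons such as withdrawal of consent, non-compliance and investigator decision.
- **The last score is not simply discarded.** After Week 2 it works through the imputed Week 3; after Week 3 the last score is a direct predictor.
- **The sizes are assumptions.** The upper end comes from exchangeable correlation, which the SAP lists as the last fallback for the MMRM. In the large-sample scenario the shift goes against the drug.

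All four stand, and they limit the claim to what is stated here.

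It can also be said that the planned sensitivity analyses cover the matter. That does not stand. The tipping-point shifts are added to values from the same Week 4 line. The reference-based analysis, although its imputation lists all visits, answers a different question.

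Finally, the printed listing has other small irregularities, such as `n impute`, so a lost word is possible though unlikely. If the signed SAP or the production program has `week_2` in that line, the point falls.

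**Conclusion.** The Week 4 line is wrong as written: a prescribed model for the primary endpoint leaves out an available visit, without a reason, and disagrees with its neighbouring lines and with the unstructured analysis model. It looks like a slip.

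The consequence is modest. For patients with MAR-imputed Week 4 values who leave after Week 2, the shortfall is 0 to about 2.4 points per 10 points of Week 2 deviation, towards the arm's predicted mean. The treatment difference moves by about 0.1 point or less, against a design difference of 8. These ranges rest on assumed correlations, earlier-visit SDs and dropout rates. The documents settle neither the size nor the direction for the actual trial. It should be corrected because it sits in the primary analysis, not because it threatens the conclusion.

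**What to change.** Before database lock, change the line to `regpmm(week_4 = baseline week_1 week_2 week_3)` and confirm that the production program matches. If the omission was intended, give the reason in 5.11.2.

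Optionally, let each line condition on all other visits, so that intermittent gaps also use later observed scores. This is a preference: the treatment period is inpatient and such gaps should be few.

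The cost is one word of SAP code and a rerun of the dry-run imputation, with no statistical downside. If left until after lock, SAP section 5 would require a post-lock addendum, and the primary imputation model might then be changed with results known.
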